
3.7. Inclusion Criteria

Phase 1

- 1. Diagnosis of primary pathologic stage 0–III cutaneous malignant melanoma;
- 2. From 3–36 months post-surgical treatment;
- 3. \geq 18 years old;
- 4. Access to the Internet;
- 5. Able to speak and read English;
- 6. Able to provide informed consent.

Phase 2

- 1. Diagnosis of primary pathologic stage 0–III cutaneous malignant melanoma;
- 2. From 3–24 months post-surgical treatment;
- 3. Not adherent to thorough SSE (i.e., did not check every area of the body at least once during the past 2 months) (Weinstock et al., 2004) or not adherent to sun protection recommendations (i.e., mean score < 4 [which corresponds to "often"] on a 5-point scale [from 1 = "never" to 5 = "always"] that assesses the frequency of engaging in four sun protection behaviors);
- 4. \geq 18 years old;
- 5. Access to a computer connected to the Internet;
- 6. Able to speak and read English;
- 7. Able to provide informed consent.

Phase 3: Qualitative Interviews

- 1. Diagnosis of primary pathologic stage 0-III cutaneous malignant melanoma
- 2. Completed at least the How to Use Tutorial of the ITW
- 3. > 18 years old
- 4. Able to speak and read English;
- 5. Able to provide informed consent.

3.8. Participant Recruitment and Consent Procedures

At Rutgers CINJ/RWJMS, potentially eligible individuals will be identified through electronic chart review (by research team members), from registrars at the tumor registry, clinical records (such as pharmacy and billing), scheduling, and from treating physicians/nurses/social workers. Potentially eligible individuals will also be identified by referral from Saint Barnabas Medical Center (see IRB approval letter from Saint Barnabas). Potentially eligible individuals at Saint Barnabas Medical Center will be identified by a member of their research team, who will send them a study information letter and medical release form (as well as a pre-paid return envelope to return the completed medical release form). For individuals at Saint Barnabas Medical Center who are mailed a study information letter (and do not call to decline further contact), a member of their study team will attempt to reach the individual by telephone to confirm they received the letter and answer any questions they may have. Another copy of the information letter along with the medical release form (and a pre-paid envelope) will be mailed a second time to individuals who have not responded. When the research staff at Saint Barnabas Medical Center receive a completed medical release form from a potentially eligible individual, the form will be sent via fax or secure email to the Rutgers research team, who will handle all subsequent study-related interactions with the individual (including determination of eligibility and consenting of eligible/interested individuals). Potentially eligible individuals will also be identified through electronic chart review at the NJSCR. Potentially eligible individuals at the NJSCR will be identified by a research NJSCR team member who will contact the physician of record for each patient. An information letter will be mailed to the physician describing the study and that the NJSCR team member will be contacting their patient for participation. The physician is requested to notify the NJSCR team member within two weeks if there is any reason that the individual should not be contacted, such as death, mental illness, or severe illness. The NJSCR team member will then mail a recruitment packet to individuals who have been identified, which includes a cover letter, study information sheet, NJSCR brochure, consent form, and postage-paid return envelope (see attachments). The NJSCR staff will conduct follow-up calls 1 week after recruitment packet mailing to confirm receipt of the packet and to answer questions about the study. As necessary, a second copy of the recruitment packet will be sent. Individuals will be called 1-2 times per week up to 8 attempts before being considered a passive refuser. An individual could participate in the study by providing verbal consent at the time of phone contact or by returning a signed consent form. If verbal consent is provided, NJSCR staff will screen the individual

Protocol Version Date: 4/5/22

using the Rutgers CINJ eligibility screening questionnaire previously discussed. Team members at NJSCR will provide contact information of consented participants as well as de-identified data including, refuser ID, full surgery date (mm/dd/yyyy), melanoma stage, age, gender and refusal reason for non-respondents securely through email to the Rutgers CINJ research team. After this step, all contact will be made to individuals by the research team at Rutgers CINJ. Team members at NJSCR will also develop and maintain a database to track patient study status, and physician and patient contact. Rutgers CINJ staff will be sending a list of individuals through encrypted and secure email who have already been recruited as well as any new lists received in order to eliminate the possibility of double-approaching or consenting. Participants may also be recruited via self-referral (e.g., from individuals who learn about the study at www.clinicaltrials.gov). Regardless of the method with which potentially eligible individuals are identified, they will be emailed/mailed an introductory letter and consent form (or receive the documents in person if they are approached in person by the Rutgers research staff during a clinic visit). The letter includes a telephone number to call if the individual has any questions or does not wish to be contacted further regarding the study. For individuals who are sent a study invitation letter (and do not call to decline further contact), a member of the study team will attempt to reach the individual by telephone to ascertain their interest and eligibility. As necessary, a second copy of the introductory letter and consent form will be sent, and a member of the research team will again try to reach the person via telephone. For eligible and interested participants, a research team member will complete the informed consent process and answer any questions that arise. In Phase 2 of the project, participants will provide verbal consent during a telephone call. We have successfully used this approach in similar prior minimal risk studies. Thus, we are requesting that the IRB provide a waiver of written/signed consent for participants who provide verbal consent. Our procedure for obtaining verbal consent and documentation of that consent has been developed based on materials from the James Madison University Office of Sponsored Programs (http://www.jmu.edu/sponsprog/allforms.html) and the Office of Human Research Protection Program at UCLA (http://ohrpp.research.ucla.edu/pages/biomedical-informed-consent). Specifically, following the "Phase 2 Consent Guide and Documentation" document, the person obtaining consent will go through each section of the consent form with the participant over the telephone. Participants will be encouraged to ask any questions regarding the consent form and the study. The person obtaining consent will check off to indicate that each section of the consent form was discussed with the participant. Additionally, the person obtaining consent will sign and date the document to attest that the consent was orally presented to the participant and that the participant provided oral assurance of his/her willingness to participate in the research.

In Phase 3, we will use the same recruitment methods and study procedures as for Phase 2. Participants will provide verbal consent during a telephone call. We will be using a "Phase 3 Consent Guide and Documentation" document to obtain consent for each of the participants who take part in the study as described above.

4. Study Variables

4.1. Phase 1 Measures

After providing informed consent, participants will complete a brief survey, including demographic information and questions about their experience doing skin self-examinations and engaging in sun protection behaviors. Draft website content materials will be presented to participants in a semi-structured format and their feedback will be elicited using open- and closed-ended questions adapted from measures developed by Ritterband and colleagues (2008).

4.2. Phase 2 Measures

An overview of the study measures is shown in Table 1. We will utilize concise, psychometrically valid measures used in our prior research or that of other research groups.

	Baseline	FU 1	FU 2	FU 3
Background Variables and Correlates				
Clinical characteristics	✓			
Internet experience	✓			
Sociodemographic factors	✓			
Melanoma risk factors	✓			
Receipt of TCE	✓	✓	✓	✓
Receipt of biopsy, skin cancer diagnosis		✓	✓	✓
Distress about melanoma	✓	✓	✓	✓
Worry about melanoma recurrence	✓	✓	✓	✓
Perceived controllability of melanoma	✓	✓	✓	✓
Melanoma knowledge	✓	✓	✓	
Perceived severity of melanoma	✓	✓	✓	
Perceived risk of melanoma recurrence	✓	✓	✓	
SSE self-efficacy	✓	✓	✓	
SSE benefits and barriers	✓	✓	✓	
SSE norms	✓			
Physician SSE recommendations	✓			✓
Sun protection self-efficacy	✓	✓	✓	
Sun protection benefits and barriers	✓	✓	✓	
Sun protection norms	✓			
Automaticity of sun protection behaviors		✓	✓	✓
Physician sun protection recommendations	✓			✓
Outcome Variables				
SSE	✓	✓	✓	✓
Sun protection behaviors	✓	✓	✓	✓
Healthcare provider visits		✓	✓	✓
Intervention Evaluation and Usage				
Impact and effectiveness of the intervention		✓		
Evaluation and utility of the intervention		✓		
Website usage		✓	✓	✓

Note. TCE = total cutaneous examination; SSE = skin self-examination; FU = follow-up; FU 1 = 8 weeks post-baseline; FU 2 = 24 weeks post-baseline; FU 3 = 48 weeks post-baseline.

4.2.1. Background Variables and Correlates. Clinical characteristics that will be abstracted from the medical record include: diagnosis, time since diagnosis, disease stage, tumor thickness, tumor ulceration, mitotic index, tumor anatomic site, histologic subtype, sentinel node status, and treatment received. Patients' Internet experience will be assessed based on how often they use the Internet and their level of comfort using the Internet. Sociodemographic factors that will be assessed include the patient's age (obtained from the medical record), sex (obtained from the medical record), race/ethnicity, income, level of education, and marital/partnered status. A number of melanoma risk factors will be assessed, including eye color, natural hair color, skin color, skin reactivity to the sun, presence of freckling, number of moles, history of sunburns, indoor UV tanning, and family history of melanoma (Glanz et al., 2008; Lazovich et al., 2008). Patients will also be asked to indicate when they last had a TCE performed by a physician and the reason for the examination (e.g., routine check-up, because the patient noticed something suspicious on his/her skin). In the 8, 24, and 48 week surveys, participants will be asked whether they had all or part of a mole or growth removed in the intervening time period and whether they were diagnosed with a new or recurrent skin cancer. Distress about melanoma, worry about melanoma recurrence, and perceived controllability of melanoma will be measured using standard items (Manne & Lessin, 2006; Moss-Morris et al., 2002; Vickberg, 2003).

Protocol Version Date: 4/5/22

Melanoma knowledge will be measured using a set of true-false items that assess knowledge about the disease and its risk factors (Manne & Lessin, 2006), as well as items regarding knowledge of the ABCDEF guide to melanoma (Coups et al., 2016; Gillen et al., 2011). Established scales will be used to assess perceived severity and risk of melanoma, SSE self-efficacy (i.e., patient's confidence in being able to perform SSE), SSE benefits and barriers, and SSE norms (Coups et al., 2011; Manne & Lessin, 2006; Mullens et al., 2004; Robinson et al., 2008; Weinstein et al., 2007). With regard to physician SSE recommendations, a series of yes/no questions will ask whether a doctor suggested the participant perform SSE, had shown the participant how to do a SSE, and had shown the patient what a melanoma lesion looks like. Sun protection self-efficacy (i.e., confidence in being able to engage in various sun protection behaviors), sun protection benefits and barriers, and sun protection norms will be measured using established measures (Azzarello & Jacobsen, 2007; Bränström et al., 2010; Manne & Lessin, 2006). Automaticity of sun protection behaviors will be assessed using the 4-item Self-Report Behavioral Automaticity Index (Gardner et al., 2012). Physician sun protection recommendations will be assessed using yes/no questions.

4.2.2. Outcome Variables. Participants will indicate whether they checked any part of their body for early signs of skin cancer in the last 12 months (for the baseline survey), 2 months (for the 8 week survey), 4 months (for the 24 week survey), or 6 months (for the 48 week survey). Individuals reporting checking their skin one or more times will indicate the number of times they checked their skin during the corresponding time frame, the last time they checked their body, and the body parts that they thoroughly examined (i.e., systematically and deliberately examined the skin) during their most recent check. This measurement approach has been shown to have excellent reliability and validity in prior research (Weinstock et al., 1999; Weinstock et al., 2004). For analytic purposes, the primary SSE outcome will be performance of thorough SSE, defined as thoroughly examining each area of the body during the most recent skin self-check in the past 2 months (Weinstock et al., 2004). We focus on thorough SSE as the primary SSE outcome, as greater SSE thoroughness is associated with detection of thinner tumors (Pollitt et al., 2009) and improved prognosis (Moore Dalal et al., 2008). The secondary SSE outcomes we will examine include thoroughly examining each area of the body during the most recent skin self-check in the past 1 month, the number of SSEs performed (regardless of their thoroughness) and the number of body areas examined. Participants will also indicate whether, the last time they did SSE, they used a mirror, had someone else help them, or used a body mole map. Participants will rate how often they engage in each of four sun protection behaviors when outside on a sunny day: wearing sunscreen with an SPF \geq 30, wearing a long-sleeved shirt, wearing a wide-brimmed hat, and staying in the shade (Glanz et al., 2008). The primary sun protection outcome will be the mean rating of the four items (sun protection behavior index). The frequency of engaging in each individual sun protection behavior will be examined as secondary outcomes. Additionally, as secondary outcomes, participants will rate how often they use sunglasses, wear long pants, and spend time in the sun in order to get a tan (Glanz et al., 2008), and the number of sunburns they had. As an exploratory outcome, at the 48 week survey, participants will indicate whether, and if so how many times, they indoor tanned in the past year. Participants will also be asked to report any visits to healthcare providers related to skin surveillance, which will be examined as an exploratory outcome. They will also be asked to report any biopsies conducted and diagnosis of new or recurrent skin cancers. Data from the medical record will be abstracted to identify patients' visits to their Rutgers CINJ, Rutgers RWJMS, or Saint Barnabas Medical Center healthcare provider.

4.2.3. Intervention Evaluation and Usage. A set of measures developed by Ritterband and colleagues (2008) will be used to evaluate the intervention and will include all aspects of the ITW. These include the Perceived Internet Impact and Effectiveness Questionnaire, the Internet Evaluation and Perceived Utility Questionnaire, and the Internet Intervention Adherence Questionnaire. Participants will also complete a series of questions that will ask them whether they viewed or shared the website information with anyone else (e.g., family members or friends). Objective information about each participant's use of the ITW be collected automatically and unobtrusively on the study web server. Website usage factors that will be

examined include the number of visits to the website, the number of monthly skin self-checks completed, the number of updates to the sun-safe action plan, and starting/completing the remaining sections of the website (Introduction; Getting Ready to Do a Skin Self-Check; Practice Sun-Safe Behaviors) (Danaher et al., 2008; Danaher & Seeley, 2009).

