3.2. Phase 2: RCT of the Efficacy of the Intervention

Consented patients will be provided with a link to a secure, password-protected website to complete a baseline survey. After completing the survey online, patients will automatically be randomized to the ITW or Usual Care condition. Patients will be stratified according to disease stage and time since diagnosis (3–<14 months vs. 14–24 months) and then, within strata, block randomized using blocks of four or six patients. The study biostatistician, [name], was responsible for creating the randomization schedule and overseeing the randomization process, following standard operating procedures of the Rutgers CINJ Biometrics Shared Resource. After 8 weeks, study participants will be prompted (via email, as well as by telephone, text message [with their permission] and mail, as necessary) to complete an online survey (follow-up 1), followed by additional online surveys 24 weeks (follow-up 2) and 48 weeks post-baseline (follow-up 3). The estimated time to complete each online survey varies from 40 minutes for the baseline to 20 minutes for the follow-up 3 survey.

Participants randomized to the ITW condition will be provided with a link to the intervention website, which they will be free to access any time throughout their study participation. To promote usage of the website, the modules of the ITW will be available to participants on a staggered basis using event- and time-based triggers. Specifically, an initial set of modules will be available to participants immediately. Once those modules have been completed (which we anticipate will take participants no longer than 2 weeks), a final module will be introduced after one week. This approach of introducing website intervention content in a staggered manner has been shown to facilitate greater use of, and exposure to, health promotion websites (Brouwer et al., 2011). We anticipate that each module will take from 30–40 minutes to complete, although participants will be encouraged to review each module regularly. Key elements of the ITW will be available (for example, as fully formatted .pdf documents) for participants to download and print.

Participants randomized to the Usual Care condition will receive no additional intervention aside from their usual non-study care. At the end of their participation in the study, participants in the Usual Care group will be offered the ITW intervention.

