3.6. Sample Size

Up to 30 individuals will take part in Phase 1 of the project. For Phase 2 of the project, we will recruit 420 participants. For Phase 3 of the project, we will recruit up to 50 participants. For the Phase 2 RCT study,

we conducted power calculations for the primary and secondary aims. (We did not conduct power calculations for Aim 3 because it is an exploratory aim.) For the primary aim (intervention efficacy), there are two primary outcomes: engagement in thorough SSE (binary outcome) and sun protection behavior index (continuous score) at 24 weeks post-baseline. At baseline, we anticipate that 9% of participants will be adherent to thorough SSE. Based on our own and others' prior research (Glanz et al., 2010; Janda et al., 2011; Manne et al., 2010; Weinstock et al., 2007), we anticipate that the rate of adherence to thorough SSE at 24 weeks post-baseline will be ≥35% in the ITW group and this will be at least 15 percentage points higher than the adherence rate in the Usual Care group. An increase in SSE of this magnitude would be considered a successful rate. We assume proportions of individuals completing SSEs are compared between treatments using a z-test. Allowing for 10% dropout at 24 weeks (a rate comparable to that experienced in our prior research; Manne et al., 2010) and an adherence rate to thorough SSE of up to 20% in the Usual Care group at 24 weeks post-baseline (which is at the upper end of what might be expected), 153 individuals would need to be recruited in each group to obtain 80% power. Power calculations for the sun protection behaviors outcome are based on results of prior tailored interventions, including our own (Glanz et al., 2010; Manne et al., 2010). In our prior RCT, sun protection scores at baseline were 2.8 for both groups and increased to 3.2 and 3.4 for the generic and tailored interventions, respectively. Given that the Usual Care control group in the current RCT is not an active control (the generic intervention in the prior study was an active control), we assume that the sun protection scores in that group would increase to a maximum of 3.0. Standard deviations were, on average, 0.66 at baseline and 0.76 at follow-up. We assume a correlation between baseline and follow-up measures of 0.60. Under these assumptions, recruiting 153 individuals to each group would provide more than 80% power to detect differences in changes in sun protection scores from baseline to 24 weeks post-baseline. For the secondary aim (intervention mediators), we utilized sample size tables for mediated effects based on simulation studies that model the two pieces of the mediating path (from intervention group assignment to mediating variable and from mediating variable to outcome) (Fritz & Mackinnon, 2007). Based on the results of relevant prior research, we conservatively assume that one of the two paths will have a regression coefficient of at least .14 (a small effect, according to Cohen's [1998] criteria) and the other will have a regression coefficient of at least .26 (a small-to-moderate effect). Under those assumptions, and allowing for 10% dropout at 24 weeks, recruiting 210 individuals to each group would provide 80% power to detect mediational effects (Fritz & Mackinnon, 2007). Overall, based on a consideration of the aforementioned factors, we will recruit 210 individuals to each of the ITW and Usual Care groups, for a total sample size of N = 420, which will provide at least 80% power for the primary and secondary aims. We anticipate that at least 378 of the 420 patients (i.e., 90%) will complete the 24 weeks post-baseline assessment and 357 (85%) will complete the 48 weeks post-baseline assessment.

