Using intent-to-treat analyses, we will compare engagement in thorough SSE and the sun protection behavior index for individuals in the ITW versus Usual Care, with the outcomes at 24 weeks as the primary focus. To handle missing data due to participant dropout, weighted generalized estimating equations (Little & Rubin, 2002; Preisser et al., 2002; Robins et al., 1995), with a logit link for SSE (a binary variable) and an identity link for the sun protection behavior index, will be used to estimate the treatment effect with weights proportional to the inverse of the estimated probability of dropout. Score tests and estimates of regression coefficients for the treatment indicator variable will assess the effect of the intervention. Sensitivity analyses will examine the effect of intervention at follow-up controlling for any demographic information that differs significantly by intervention group at baseline. These analyses are appropriate under the assumption that dropout is missing at random (MAR). Secondary analyses will use multiple imputation to examine the estimated treatment effect under different scenarios assuming the dropout is missing not at random (MNAR). In particular, for the sun protection behavior index, the mean for treated dropouts will be assumed equal to the estimated mean for Usual Care non-dropouts plus a sensitivity parameter, set at values of 25%, 50%, 75% and 100% of the estimated treatment effect (representing scenarios ranging from dropouts experiencing almost all to none of the estimated treatment effect). These analyses provide a picture of potential bias due to informative dropout (Little, 1994; Minini & Chavance, 2004a, 2004b; National Research Council, 2010). Additional multilevel models (Raudenbush, 2003) will examine the effect of the intervention on changes in thorough SSE and sun protection behaviors over time, comparing changes across 8, 24 and 48 weeks. Specifically, generalized estimating equations will be used for estimation and testing (Liang & Zeger, 1986; Ukoumunne & Thompson, 2001). Additional analyses will focus on the effect of the intervention on the number of SSEs performed, the number of body areas examined, and the individual sun protection behaviors (wearing sunscreen with an SPF \geq 30, wearing a long-sleeved shirt, wearing a wide-brimmed hat, and staying in the shade). Analyses will also focus on the effect of the intervention on use of sunglasses, wearing long pants, spending time in the sun in order to get a tan, and the number of sunburns.

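### No sun-protection model includes season, although the 24-week primary measure falls about half a year from baseline: the arm comparison stays unbiased, but precision and a clear reading of the time course are lost

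*Combined protocol and SAP*

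**What the plan says.** Section 4.2.2 (Outcome Variables) defines the sun items: "Participants will rate how often they engage in each of four sun protection behaviors when outside on a sunny day". The index is their average: "The primary sun protection outcome will be the mean rating of the four items (sun protection behavior index". Sunburns are a secondary outcome, worded only as "and the number of sunburns they had". The same section gives recall periods for the skin self-examination (SSE) items and for indoor tanning, but none for the four sun items or for sunburns.

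After the 8-week survey, section 3.2 schedules "additional online surveys 24 weeks (follow-up 2) and 48 weeks post-baseline (follow-up 3". Section 5.1 compares the arms "with the outcomes at 24 weeks as the primary focus", using weighted generalized estimating equations (GEE), and adds models "comparing changes across 8, 24 and 48 weeks". The only covariate adjustment in 5.1 is a sensitivity analysis for demographic variables that differ at baseline.

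Season and calendar date are absent from the strata (3.2), the models (5.1), the moderators (5.3) and the recruitment rules (3.8). The enrolment period is not stated. The recruiting institutions and the registry named in 3.5 are in New Jersey.

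**The concern.** Sunscreen, long sleeves, a wide-brimmed hat and shade can plausibly vary with the time of year. Someone who enrols in summer gives the primary measure in winter, and the reverse, while the 48-week survey comes back close to the baseline season. Three things are at stake.

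- Precision: seasonal variation that is not modelled sits in the residual. It also works against the assumed baseline-to-follow-up correlation, because the two measures are nearly in opposite phase.
- The time course: survey wave and season are linked within each participant. If enrolment is uneven over the year, the link does not average out.
- Sunburns: with no stated window, it is unclear whether each participant's count covers any summer.

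**Working it through.** **Inputs from section 3.6.** Standard deviations (SDs) are 0.66 at baseline and 0.76 at follow-up. On the correlation: "We assume a correlation between baseline and follow-up measures of 0.60". Prior scores "increased to 3.2 and 3.4 for the generic and tailored interventions, respectively", and Usual Care is put at no more than 3.0, so the implied difference is 3.4 − 3.0 = 0.4. Recruitment is 210 per group; with 10% dropout, 189 per group remain at 24 weeks. Assumption: two-sided 5% level, which the plan does not state.

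**The plan's own figure.** Change SD = √(0.66² + 0.76² − 2·0.60·0.66·0.76) = √0.411 = 0.641. With 153 per group less 10%, 137 are evaluable. Power = Φ(0.4/(0.641·√(2/137)) − 1.96) = Φ(3.20) = 99.9%. This agrees with the claim of more than 80%.

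**Phase.** 24/52.18 = 0.46 of a year, or 166°, with cosine −0.97. The 8- and 48-week surveys fall at 55° and 331°.

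**Adding a season (assumption).** Take a yearly cosine of amplitude A points, with enrolment spread over the year. It adds A²/2 to the variance at each wave and −0.97·A²/2 to the covariance. Then:
- 24-week score variance = 0.5776 + A²/2
- change variance = 0.411 + A²(1 + 0.97)
- baseline-adjusted variance = follow-up variance − covariance²/baseline variance

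| A | Correlation | SD, 24-week score | SD, baseline-adjusted | SD, change |
|---|---|---|---|---|
| 0 | 0.60 | 0.760 | 0.608 | 0.641 |
| 0.1 | 0.58 | 0.763 (+0.4%) | 0.619 (+2%) | 0.656 (+2%) |
| 0.2 | 0.54 | 0.773 (+1.7%) | 0.651 (+7%) | 0.700 (+9%) |
| 0.3 | 0.47 | 0.789 (+3.8%) | 0.696 (+15%) | 0.767 (+20%) |

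Standard errors rise by the same percentages.

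**Power.** For a difference of 0.4 at 189 per group, change-score power stays at 99.9% or more for these amplitudes. Even at A = 0.5 (a full point from peak to trough) it is 98.3%, or 93.6% at 137 per group. If the true difference were only 0.2 (assumption), change-score power at 189 per group would go from 86% to 84%, 79% and 72% for A = 0.1, 0.2 and 0.3.

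**Bias.** A simulation used 378 evaluable participants, blocks of four and A of 0, 0.2 or 0.5, with enrolment either even over two years or squeezed into four months. Mean bias was at most 0.003 for the 24-week arm difference under no effect, and at most 0.003 for the arm difference in 8-to-24-week change. Type I error ran from 3.0% to 5.7%.

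**Time course.** In the same simulation the within-arm 8-to-24-week change was undistorted under even enrolment. With four-month enrolment starting at the seasonal peak, it shifted by about −0.05 (A = 0.2) and −0.13 (A = 0.5). Other four-month windows can do more. The largest shift is 2·sin(π·16/52.18)·[sin(π·17/52.18)/(π·17/52.18)]·A = 1.642·0.834·A = 1.37A, or 0.27 at A = 0.2. The same factor applies to the arm effect if that effect itself swings by season: with amplitude B, its change from 8 to 24 weeks could move by up to 1.37B under this extreme enrolment, and by nothing under even enrolment.

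**Sunburn windows.** The gaps between surveys are 8, 16 and 24 weeks, 48 in total (336 days). About 29 days of a year are left uncovered. Taking May to September (153 days) as summer (assumption), a participant who answers on schedule has at least 153 − 29 = 124 of those days covered.

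**The case against.** **No confounding of the arms.** A reader might infer that season confounds the arm comparisons. The documents do not support that. Section 3.2 randomises concurrently in blocks of four or six, so both arms share the same seasonal mix at each survey. With an additive season effect, the 24-week contrast, the arm-by-wave contrast and the sunburn comparison are all unbiased. This objection stands in full.

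**The primary model loses least.** Section 5.1 names neither a change score nor the baseline score as a covariate; change appears only in the power calculation in 3.6. If the primary model is read as the 24-week score alone, the loss is the smallest in the table, 0.4% to 3.8%. This also stands.

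**The amplitude is assumed.** The sunny-day condition may dampen seasonality, and long sleeves may move opposite to the other items. The SDs, taken from a prior trial, may already contain season. For the 24-week score the last point changes little: 0.76/√(0.5776 − A²/2) gives 0.4%, 1.8% and 4.1%. For change scores the documents do not settle it.

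**Sunburn dilution.** A reader might infer that many participants have no chance of a sunburn before the 24-week survey. With a four-month window, even enrolment and a May–September summer, (7 − 4)/12 = 25% would have no summer day. But that window is stated only for SSE, and 5.1 names no time point for sunburns. Fewer events would cost precision in both arms; they would not bias the comparison.

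**Conclusion.** The point holds as one of efficiency and interpretation. The primary sun measure falls about half a year from baseline, and no sun model uses season. The validity of the arm comparison and the stated power for 0.4 points are not in question. The precision cost depends on an amplitude that the documents do not give. Over 0.1 to 0.3 points it is negligible to small for the 24-week score alone, and material (up to 15% or 20% on the standard error) only for baseline-adjusted or change-score analyses.

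Within-arm trends can mix with season when enrolment is uneven over the year. Reading a changing arm effect as decay or maintenance is unsafe only if, in addition, the intervention effect varies by season. The documents neither establish nor exclude either condition. The sunburn recall window is a plain gap.

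**What to change.** In section 5.1:

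- Add annual sine and cosine terms, or a four-season factor, to every sun-protection and sunburn model. Base them on enrolment date or scheduled survey date, since the actual completion date arises after randomisation. In the 24-week model a fixed 24-week shift only rotates the sine–cosine pair, so either date gives the same fit.
- In the 8/24/48-week models, compute the terms for each wave. Fit arm-by-season as a supportive check before interpreting arm-by-wave.
- Analyse sunburns over the whole follow-up, about 48 weeks, with each survey asking about the time since the previous one. State that window in 4.2.2. Borrowing the SSE windows of 2, 4 and 6 months (8.7, 17.4 and 26.1 weeks) would exceed the 8-, 16- and 24-week gaps by 0.7, 1.4 and 2.1 weeks and could double-count burns.

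The cost is two or three extra parameters per model, with a similar number for the supportive check. The dates follow from enrolment and the survey schedule. The sunburn total needs all three follow-up surveys or the planned missing-data handling, and its wording can change only for surveys not yet sent; otherwise, state the window that was used.
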